7. BACKGROUND AND SIGNIFICANCE

Light stroking and deep pressure (compression) touch are components of numerous complementary health techniques but especially massage therapy, which has been shown to significantly reduce depression, stress, and pain [1, 10]. Deep pressure touch reduces anxiety [11] as well as induced pain and unpleasant affect [12]. Both light stroking and deep pressure have shown analgesic effects in healthy adults in a laboratory setting [6, 7]. Further, moderate (versus light) pressure is necessary for the effects of massage therapy [4], and compared to light pressure or vibration, leads to greater reduction of stress and anxiety and higher ratings of pleasantness [5]. While neutral touch is known to reduce pain perception in a segmental manner (within dermatomes) [13], the relative benefits of affective touch are unknown. Furthermore, massage therapy is a complementary therapy frequently sought out by individuals with chronic pain [14], but little is known about its analgesic benefits in individuals with chronic pain. Pleasant touch has been linked through microneurography to the activation of C low-threshold mechanoreceptor (C-LTMR) fibers, unmyelinated sensory afferents that respond to slow gentle stroking of the skin and activate opioidergic brain regions including the insula and cingulate cortex [3, 15]. We previously showed that individuals with Fibromyalgia

(FM), a chronic pain condition, show reduced pleasantness of light stroking touch. This same effect has been shown now in patients with low back pain (LBP) [8]. However, the reasons for this reduction in pleasantness of affective touch are not known. Further, it is not known whether deep pressure touch is also less pleasant for patients with chronic pain. It is also not known whether pleasant touch has a reduced (or enhanced) analgesic benefit for patients with chronic pain. There is thus a significant gap in our understanding of the processing of pleasant touch in individuals with chronic pain. The proposed R00 research will identify factors underlying the alteration of affective touch perception observed in individuals with chronic pain. Further, it will identify whether the analgesic benefits of light gentle stroking, deep pressure, and neutral touch are the same in patients with chronic pain as in healthy adults, and whether the nonsegmental analgesic effect is related to the perception of touch pleasantness. The expected contribution of the proposed research is an understanding of the analgesic effects of light and deep pressure touch in healthy individuals and in chronic pain. This contribution will be significant because it will provide knowledge of the perceptual and analgesic effects of light and deep pressure touch (components of numerous complementary therapies) in people with and without chronic pain. This contribution will inform subsequent research on manual touch therapies by providing background information about the modulation of pain by affective touch, and differences in individuals with chronic pain. This should provide greater understanding of how complementary techniques work in chronic pain.

The proposed research will compare the analgesic effects of light and deep pressure touch to those of neutral touch, determine whether the effects are direct (segmental), and determine whether these effects differ in individuals with chronic pain conditions. It will also determine which factors predict the blunted affective touch perception observed in patients with chronic pain. Finally, it will include continuous respiration monitoring during affective and pain testing to determine whether slower respiration rate underlies (mediates) the analgesic effects of pleasant touch. The central hypothesis is that both light and deep pressure pleasantness are blunted in individuals with chronic pain primarily due to psychological factors, and that the analgesic effects of pleasant touch will also be reduced in patients with chronic pain. Further, we predict that pleasant touch will exert greater (nonsegmental) analgesic benefits than neutral touch, and that this analgesic effect will correlate with the pleasantness of touch. This research will advance our understanding of the mechanisms of massage therapy and its effect on those who suffer from chronic pain.

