
The proposed research is the subject of a pending R00 award and will determine whether light and deep pressure touch have comparable analgesic effects, and whether these effects differ in individuals with chronic pain conditions. It will also determine which factors predict the blunted affective touch perception observed in patients with chronic pain. The central hypothesis is that both light and deep pressure touch exert analgesic benefits, and that these analgesic effects will correlate with the pleasantness of touch. Further, we predict that the analgesic effects of pleasant touch will be reduced in patients with chronic pain, who experience reduced touch pleasantness. This research will advance our understanding of the mechanisms of massage therapy and its effect on those who suffer from chronic pain.

Aim 1 (R00): Determine why individuals with chronic pain show reduced C-LTMR-related touch pleasantness.

Hypotheses: I hypothesize that blunted pleasantness of C-LTMR and deep pressure touch in individuals with chronic pain will be predicted by psychological factors including depression and trauma history (due to the impact of these factors on the μ -opioid system, e.g. [9]).

Aim 2 (R00): Determine whether the analgesic effects of light and deep pressure touch are reduced in individuals with chronic pain, and whether analgesia correlates with pleasantness perception.

Hypotheses: I hypothesize that concurrent or recent administration of light or deep pressure pleasant touch will reduce the perceived pain of a phasic heat stimulus, and that this effect will be reduced in chronic pain patients. Further, I predict that the analgesic effect of affective touch will be correlated with the perceived pleasantness of the touch.

Sub-aim 2b: Determine whether CPM effects of pleasant touch are related to CPM effects of pain.

Hypotheses: I hypothesize that the CPM efficiency for painful and pleasant touch will not be correlated across participants, suggesting divergent mechanisms.

Sub-aim 2c: Determine whether analgesic effects of light stroking or deep pressure are mediated by reductions in respiration rate.

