9. RESEARCH DESIGN AND METHODS

All procedures in this study are conducted solely for research purposes.

This proposed NIH-sponsored psychophysical and neuroimaging study includes two behavioral testing sessions, as well as one MRI session for a subset of participants. In this experiment we are studying sensory mechanisms supporting the modulation of pain by affective touch, and comparing them between individuals with and without the chronic pain condition Fibromyalgia (FM).

If the study will maintain a database for future uses (uses other than those specifically stated in this Research Plan), this must be clearly stated along with what information will be retained in the database and provide future examples of the potential future uses of the information.

Pre-Study Screening Procedures

Interested individuals will complete the phone screening. This includes demographic information as well as questions targeting inclusion and exclusion criteria (see Phone Screen Attachment).

Data Collection:

The following information will be collected from all participants: name, date of birth, age, gender, ethnicity, telephone number, email address, medical record number (will be deleted from study file once review of medical records is complete), diagnosis, condition, current/previous drug regimen, and handedness.

Consent & REDCap Intake

Prior to session 1, a member of the study team will email participants a REDCap link to digitally sign the consent form remotely. A member of the study team will schedule a phone or video call with participants to simultaneously discuss the consent form and answer any questions that may arise. After digitally signing the consent form and a HIPAA authorization form, history of their opiate use will be collected by asking participants to name every opiate medication they have taken previously and duration of use. Approximately one week prior to Session 1, participants will then be directed to REDCap to complete the following study questionnaires.

Study Assessments

Participants will complete the following questionnaires in REDCap:

- Chronic Pain Grade Questionnaire [16]
- Fibromyalgia Impact Questionnaire (Bennett, Friend et al. 2009)
- Childhood Trauma Questionnaire [17]
- Hospital Anxiety and Depression Scale (HADS) [18]
- Longing for Interpersonal Touch Picture Questionnaire [19]
- The Pittsburgh Sleep Quality Index (PSQI) [20]: This is a 10-item assessment designed to measure quality and patterns of sleep in adults.

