We expect that FM patients will show reduced pleasantness of C-LTMR-optimal touch compared to healthy individuals as found in FM patients in [3] and LBP patients in [8]. We hypothesize that current depression and trauma history will be significant predictors of blunted C-LTMR touch pleasantness. Based on an effect size F^2 of 0.15, three predictors, alpha of 0.05, and power 0.8, this study will require $N = 77$ participants. We will round up to $N = 80$ and include $N = 40$ FM patients and $N = 40$ healthy controls. Based on effect sizes observed in [3] and [8], this sample size will also be sufficient for the comparisons of pleasant touch.

Furthermore, we expect that FM patients will show reduced analgesic benefit of pleasant touch compared to healthy controls, due to reduced touch pleasantness ratings and our theorized relationship between touch pleasantness perception and analgesia, and due to reduced endogenous pain modulation evidenced in the CPM paradigm. We expect reduced analgesic effects of touch pleasantness in FM due to altered pleasant touch perception in FM (and LBP) [3, 8]. The studies showing analgesic effects of affective touch showed effect sizes of approximately $d = 0.6$ [6] and $d > 2$ (for the large compression area) [7], respectively. We would need 24 participants to demonstrate the smaller effect size in each group (alpha of 0.05, power of 0.8). No previous study has examined how pleasant touch modulates pain in chronic pain compared to healthy adults. To observe a difference in affective pain modulation between patients and healthy controls, based on the average large effect size of 0.78 seen across studies in [27] for CPM, this study would require 27 participants in each group, so the 40 participants calculated for each group will be sufficient. The MRI portion of the study will be a pilot study ($N = 20$), intended to provide preliminary data for future grant applications.

Data Analyses and Interpretation

Scores on the depression and trauma history questionnaires will be used as linear regressors to predict ratings of gentle brushing pleasantness.

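### The Aim 1 model, as described, names no fibromyalgia severity term, so it cannot separate depression from worse disease or show that blunting is mainly psychological

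*Combined protocol and SAP*

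**What the plan says.** Section 6 (Specific Aims) sets Aim 1 as "Determine why individuals with chronic pain show reduced C-LTMR-related touch pleasantness". Its hypothesis is that the blunting "will be predicted by psychological factors including depression and trauma history". Section 7 (Background and Significance) goes further. It gives as the central hypothesis that light and deep pressure pleasantness "are blunted in individuals with chronic pain primarily due to psychological factors".

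The analysis text in Section 9 (Data Analyses and Interpretation) gives Aim 1 one sentence: "Scores on the depression and trauma history questionnaires will be used as linear regressors to predict ratings of gentle brushing pleasantness". It names no severity, impact or group term.

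The sample size paragraph in Section 9 is "Based on an effect size F^2 of 0.15, three predictors, alpha of 0.05, and power 0.8", which gives 77. It continues: "We will round up to $N = 80$ and include $N = 40$ FM patients and $N = 40$ healthy controls". It counts three predictors where the analysis names two, and the third is identified nowhere.

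Section 9 (Study Assessments) lists the Chronic Pain Grade Questionnaire and the Fibromyalgia Impact Questionnaire among the instruments that participants complete. Neither is assigned to an analysis. Section 10 requires controls to be free of current and chronic pain, and matches the groups on age and sex only.

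**The concern.** To say that something is mainly psychological is to compare it with other explanations, and the obvious rival is how severe the pain condition is. A model whose named regressors are both psychological cannot make that comparison.

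If patients with worse FM are both more depressed and less responsive to pleasant touch, the depression coefficient picks up the severity effect and Aim 1 reports a psychological predictor. If the unnamed third predictor is group, that removes the average difference between patients and controls. It leaves the variation in severity among patients, which is where depression and severity can move together.

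At stake is the interpretation of the study's main explanatory result. Feasibility and the touch-analgesia comparisons of Aim 2 are not affected.

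**Working it through.** **1. The plan's own figure.** Inputs from Section 9: f² = 0.15, three predictors, alpha 0.05, power 0.80. For the overall regression F test, noncentrality = f² × N, with p and N − p − 1 degrees of freedom.
- p = 3: power is 0.796 at N = 76 and 0.802 at N = 77. The stated 77 is reproduced, and power at N = 80 is 0.82.
- p = 2 (the regressors actually named): N = 68.
- p = 4 (one more term): N = 85, and power at N = 80 is 0.77.

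The sample size was therefore computed for a model with one more term than the analysis text describes.

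**2. Assumptions for the confounding check.** The documents give no correlations among depression, severity and pleasantness. I assume depression–severity r = 0.4 to 0.6, severity–pleasantness r = −0.3 to −0.4, and no direct effect of depression.

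**3. Induced correlation.** With no direct effect, r(depression, pleasantness) is the product of the two:
- low end: 0.4 × (−0.3) = −0.12
- high end: 0.6 × (−0.4) = −0.24

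**4. Chance of p < 0.05 in the 40 FM participants (Fisher z).** The expected z is atanh(|r|) × √(n − 3), with √37 = 6.083.
- r = 0.12: 0.1206 × 6.083 = 0.733. Φ(0.733 − 1.96) + Φ(−0.733 − 1.96) = 0.110 + 0.004 = 0.11.
- r = 0.24: 0.2448 × 6.083 = 1.489. Φ(1.489 − 1.96) + Φ(−1.489 − 1.96) = 0.319 + less than 0.001 = 0.32.

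Simulating the depression-plus-trauma regression itself (depression–trauma r assumed 0.3) gives about 10% and 29% at the two ends. Adding severity returns the rate to about 5%.

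**5. Pooled sample with group as the third predictor.** There are 40 FM participants and 40 controls, and severity varies only among the FM participants because controls are pain-free. Simulations with slightly different set-ups gave 7% to 16% and 8% to 18%. With severity added to group, the rate is about 5%.

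**6. Wider assumptions.** With depression–severity r of 0.3 to 0.7, a severity slope of −0.3 to −0.5, and FM patients 1 SD higher on depression and 0.6 SD lower on pleasantness, the pooled rates for depression are:

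| Model | p < 0.05 |
|---|---|
| Depression + trauma | 25% to 58% |
| + group | 7% to 27% |
| + group + severity | about 5% |

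Much of the first row is the patient–control difference, which is a separate matter from severity. The second row is the part a group term leaves behind.

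**7. What an adjusted FM-only model can detect.** With n = 40 and three predictors, power for a single coefficient is 66% at partial f² = 0.15, 49% at 0.10 and 28% at 0.05. It reaches 80% at f² = 0.207, a partial R-squared of 0.207 / 1.207 = 0.17.

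**The case against.** **The strong wording is not in Aim 1.** A reader might infer that Aim 1 commits the study to proving a mainly psychological cause. It does not: Section 6 says the factors will predict blunting, and no success criterion depends on the stronger word. This stands. But Section 7 calls the stronger statement the central hypothesis, and the Aim 1 regression is the only analysis that bears on it.

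**The third predictor might be severity.** The documents do not support saying that severity is excluded, only that it is not named. If severity was intended, the remedy is to write it down. If group was intended, step 5 shows that the problem shrinks but remains.

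**The size could be made to look larger.** Applying the same correlations to all 80 participants would give about 18% to 57%. That reading does not fit the design, because it needs severity to vary across all 80 and half of them are pain-free by eligibility.

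**Severity may be a mediator.** Depression may worsen pain, which in turn dulls touch. Adjusting would then remove part of the effect of interest. This stands, and it is why adjusted and unadjusted estimates belong side by side.

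**Requiring significance after adjustment would be unsafe.** This also stands: at 66% power for partial f² = 0.15, a real psychological effect would often fail. Surviving adjustment would not in itself show that psychology is the primary factor either.

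**Severity is one rival among several.** Sleep, catastrophizing and drug regimen are also collected. That is fair, but severity is the most direct alternative to a psychological explanation, and two instruments for it are already in the battery.

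**Conclusion.** The point holds as a matter of interpretation and prespecification. As described, the Aim 1 model can credit depression with an effect of worse FM, and it cannot support a claim that psychological factors are the primary reason for blunting. With no direct depression effect and the correlations assumed above, a depression result at p < 0.05 is expected in roughly 10% to 32% of FM-only analyses and roughly 7% to 18% of pooled analyses with a group term, against 5%.

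These figures show direction and plausible range. They rest wholly on assumed correlations and do not show that a depression finding in this study would be spurious. The change is a cheap improvement and not a condition for the study to proceed.

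**What to change.** 1. Name the third predictor in the Aim 1 model, so that the analysis text agrees with the sample size.
2. Prespecify a supporting regression of brushing pleasantness in the 40 FM participants on depression, trauma and Chronic Pain Grade pain intensity. Alternatively, use a pooled model with group plus severity centred within FM. Uncentred severity is nearly collinear with group, because controls sit at its floor.
3. Report the depression and trauma coefficients with confidence intervals, with and without severity, and the unique R-squared of each term. State that severity may be a confounder or a mediator and that this design cannot tell which.
4. Do not use significance after adjustment as the decision rule. Word the conclusion as association, and base any statement about the primary factor on the comparison of unique contributions.
5. Bring the causal wording in Section 7 into line with Section 6.

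Cost: one extra regression on data already collected, with no new participants or procedures. The FM-only estimates will have wide limits (80% power only for a partial f² of about 0.21). In the pooled alternative with four predictors, overall power at N = 80 falls from 0.82 to 0.77 at f² = 0.15. A joint 2-df test of depression and trauma at partial f² = 0.15 keeps 0.87.

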8. PROGRESS REPORT

None, this is an initial application.

9. RESEARCH DESIGN AND METHODS

All procedures in this study are conducted solely for research purposes.

This proposed NIH-sponsored psychophysical and neuroimaging study includes two behavioral testing sessions, as well as one MRI session for a subset of participants. In this experiment we are studying sensory mechanisms supporting the modulation of pain by affective touch, and comparing them between individuals with and without the chronic pain condition Fibromyalgia (FM).

If the study will maintain a database for future uses (uses other than those specifically stated in this Research Plan), this must be clearly stated along with what information will be retained in the database and provide future examples of the potential future uses of the information.

Pre-Study Screening Procedures

Interested individuals will complete the phone screening. This includes demographic information as well as questions targeting inclusion and exclusion criteria (see Phone Screen Attachment).

Data Collection:

The following information will be collected from all participants: name, date of birth, age, gender, ethnicity, telephone number, email address, medical record number (will be deleted from study file once review of medical records is complete), diagnosis, condition, current/previous drug regimen, and handedness.

Consent & REDCap Intake

Prior to session 1, a member of the study team will email participants a REDCap link to digitally sign the consent form remotely. A member of the study team will schedule a phone or video call with participants to simultaneously discuss the consent form and answer any questions that may arise. After digitally signing the consent form and a HIPAA authorization form, history of their opiate use will be collected by asking participants to name every opiate medication they have taken previously and duration of use. Approximately one week prior to Session 1, participants will then be directed to REDCap to complete the following study questionnaires.

Study Assessments

Participants will complete the following questionnaires in REDCap:

- Chronic Pain Grade Questionnaire [16]
- Fibromyalgia Impact Questionnaire (Bennett, Friend et al. 2009)
- Childhood Trauma Questionnaire [17]
- Hospital Anxiety and Depression Scale (HADS) [18]
- Longing for Interpersonal Touch Picture Questionnaire [19]
- The Pittsburgh Sleep Quality Index (PSQI) [20]: This is a 10-item assessment designed to measure quality and patterns of sleep in adults.
- The Freiburg Mindfulness Inventory (FMI) [21]: This is a 14-item standard mindfulness scale to measure potential changes in mindfulness before and after intervention.
- Pain Catastrophizing Scale (PCS) [22]: This is a 13-item assessment derived from definitions of catastrophizing. The PCS yields a total score and three subscale scores assessing rumination, magnification, and helplessness in subjects.
- Chronic Pain Acceptance Questionnaire (CPAQ-R) [23]: This is a 20-item assessment designed to measure acceptance of pain. The acceptance of chronic pain is thought to reduce attempts to avoid or control pain and thus focus on engaging in valued activities.
- Pain Self Efficacy Questionnaire (PSEQ) [24]: This is a 10-item questionnaire that is designed to assess confidence people with ongoing pain have in performing activities while in pain.
- Social Connected Scale (SCS) [25]: This is a 20-item assessment designed to measure social connectedness, an attribute of the self that reflects cognitions of enduring interpersonal closeness with the social world, in participants.
- Multidimensional Assessment of Interoceptive Awareness, Version 2 (MAIA-2) [26]: This is a 37-item multidimensional instrument that includes 8 scales ranging from 3 to 7 items each. The scales are noticing, not-distracting, not-worrying, attention regulation, emotional awareness, self-regulation, body listening, and trusting.
- Self-Compassion Scale (SCS): This 24-item scale measures the degree to which one is accepting of their own suffering and shortcomings, and the desire to alleviate their suffering with patience and kindness.

Consent and REDCap surveys will occur from participants' home or other remote location and will take approximately 1 hour to complete.

Session 1

When participants arrive to the laboratory for Session 1, a urine pregnancy test will be performed for all women of childbearing potential. An opiate-focused urine drug screening will also be performed. Participants who are pregnant and/or are currently taking opiates will be dismissed. A single reschedule may be permitted for a failed drug screen, if the participant identifies having consumed poppy seeds.

Participants will be fitted with a BioNomadix RSP respiratory transducer belt and amplifier. Respiration rate will be recorded with a Biopac MP160 and digitized using AcqKnowledge software at rest and throughout the entire session.

We will then familiarize participants with our touch tasks and collect baseline ratings. A brief training will be conducted to introduce sensations and rating scales. We will then collect several rounds of ratings of approximately 1 min each of light gentle brushing (using a soft paint brush), deep pressure (using a lymphedema compression sleeve inflated to <100mmHg or a commercially available massager), a neutral touch (tapping), and heat pain using a Medoc or Thermal QST thermode. Testing will occur on the limbs in areas identified as most comfortable by patients. Participants will be asked to rate their mood at various timepoints throughout the study.

Finally, we will conduct a classic CPM paradigm with a cold water bath where participants immerse their forearm into a 12°C refrigerated circulating water bath (e.g. NESLAB Digital One RTE 7, Thermo Scientific, Newington, NH, USA) for 60 seconds. The CPM paradigm is used to test the analgesic effects of a concurrent or recent test pain stimulus on a conditioned pain stimulus. The effects of the cold-CPM paradigm will be contrasted with a modified affective-CPM paradigm in Session 2. The cold-CPM block will include: phasic heat pain (baseline), heat pain while concurrently placing hand in the cold water bath (test), and then test phasic heat perception once again (post-test), as follows:

Calibration (psychophysical testing): determine level of heat to administer that results in a verbal pain rating of 6 out of 10 (0 = no pain; 10 = intolerable pain). An ascending series of 10s-duration heat stimuli between 39 and 50C will be administered until a stimulus is rated as a 6 out of 10. If a 6 is surpassed, stimuli will be decreased in .5C increments until the rating of 6 is achieved. Ratings will be confirmed by administering a 30s stimulus and adjusted if necessary.

Baseline: Heat will be administered using a thermode for 30s. Pain intensity ratings for the heat will be collected every 10s for a total of 3 ratings.

Test: 0-30s: rate unpleasantness and intensity of the cold water stimulus. 30-60s: administer heat pain using a thermode concurrently; pain intensity rating of heat pain given every 10sec for a total of 3 ratings

Post-test: Repeat of baseline.

Session 1 will occur at the ACTRI and will take approximately 1 hour to complete.

Session 2: Affective-CPM Paradigm

A urine pregnancy (if applicable) and opiate test will be performed.

Participants will be fitted with a BioNomadix RSP respiratory transducer belt and amplifier. Respiration rate will be recorded with MP160 and digitized using AcqKnowledge at rest and throughout the entire session.

We will test the analgesic effects of light slow brushing, deep pressure, and neutral touch (tapping) on induced pain using a modified affective-CPM paradigm. In this session, we will test the effect of non-painful touch stimuli on the conditioned pain stimulus, as has been conducted by [6, 7]. Both segmental (same dermatome) and nonsegmental (different dermatome) effects will be tested in order to determine whether pain inhibition is a bottom-up neural effect or an indirect affective effect.

After identifying limb locations identified as most comfortable by patients, we will perform calibration and will administer six affective-CPM blocks in an order counterbalanced across subjects: brushing, pressure, and

tapping, repeated with testing within a segment (same dermatome) and outside a segment (different dermatome).

Calibration (psychophysical testing): Session 2 calibration will be confirmed by testing the temperature rated as a 6 in Session 1 and adjusting as necessary.

Each affective-CPM block will include: phasic heat pain (baseline), heat pain with concurrent touch stimulus (test), and then test phasic heat perception once again (post-test), as follows:

Baseline: Heat will be administered using a thermode for 30s. Pain intensity ratings for the heat will be collected every 10s for a total of 3 ratings.

Test: 0-30s: rate pleasantness and intensity of the touch stimulus (brushing, pressure, or tapping). 30-60s: administer heat pain using a thermode concurrently; pain intensity rating of heat pain given every 10sec for a total of 3 ratings

Post-test: Repeat of baseline.

Between blocks the participant will rest for approximately 10-15min until sensation has dissipated to avoid habituation to test stimuli.

Session 2 will occur at the ACTRI and will take approximately 1-2 hours to complete.

Session 3: MRI Session for healthy controls (optional, offered until $N = 20$ controls have completed MRI)

A urine pregnancy (if applicable) test will be performed.

We will test the analgesic effects of affective touch on induced pain using BOLD fMRI or arterial spin labelling (ASL) in 20 healthy participants using the same test paradigm conducted in Session 2. Neural responses will be compared during the periods of thermal heat pain with versus without concurrent or recent touch.

The MRI session will occur at the UCSD Center for Functional MRI (CfMRI) and will take approximately 2-3 hours to complete.

Timeline

Sessions may be completed on the same day or on different days according to the participant and experimenters' availability. After providing written consent (active enrollment), subjects will have 4 months to complete Sessions 1 and 2 or they may be dropped from the study if the study team cannot accommodate an extension. Any spacing of sessions is acceptable. A single reschedule may be allowed for participants who fail a drug screen due to recent consumption of poppy seeds (if not previously aware) or if there are any technical issues in the session. MRI sessions will be offered to healthy volunteers until 20 have completed the MRI session. These sessions will be filled on a first-come-first-served basis.

Outcome Measure(s)

Visual Analog Scale (VAS): Pain ratings and touch pleasant/unpleasantness ratings will be assessed in response to each sensory stimulus at baseline (Session 1) and during the baseline and post-tests in the cold- and affective-CPM blocks. On each scale the minimum rating will be designated as "no pain/unpleasantness/pleasantness" and the maximum will be labeled as "most intense imaginable" or "most unpleasant/pleasant imaginable."

Cerebral blood flow (average blood perfusion; mL blood/100 grams tissue/minute): changes in cerebral blood flow (CBF) will be assessed during arterial spin labeling MRI to compare processing of pain before, during, and after affective or control touch conditions. The MRI portion of the study is a pilot study.

Sample Size Determination & Power

We expect that FM patients will show reduced pleasantness of C-LTMR-optimal touch compared to healthy individuals as found in FM patients in [3] and LBP patients in [8]. We hypothesize that current depression and trauma history will be significant predictors of blunted C-LTMR touch pleasantness. Based on an effect size F^2 of 0.15, three predictors, alpha of 0.05, and power 0.8, this study will require $N = 77$ participants. We will round up to $N = 80$ and include $N = 40$ FM patients and $N = 40$ healthy controls. Based on effect sizes observed in [3] and [8], this sample size will also be sufficient for the comparisons of pleasant touch.

Furthermore, we expect that FM patients will show reduced analgesic benefit of pleasant touch compared to healthy controls, due to reduced touch pleasantness ratings and our theorized relationship between touch pleasantness perception and analgesia, and due to reduced endogenous pain modulation evidenced in the CPM paradigm. We expect reduced analgesic effects of touch pleasantness in FM due to altered pleasant touch perception in FM (and LBP) [3, 8]. The studies showing analgesic effects of affective touch showed effect sizes of approximately $d = 0.6$ [6] and $d > 2$ (for the large compression area) [7], respectively. We would need 24 participants to demonstrate the smaller effect size in each group (alpha of 0.05, power of 0.8). No previous study has examined how pleasant touch modulates pain in chronic pain compared to healthy adults. To observe a difference in affective pain modulation between patients and healthy controls, based on the average large effect size of 0.78 seen across studies in [27] for CPM, this study would require 27 participants in each group, so the 40 participants calculated for each group will be sufficient. The MRI portion of the study will be a pilot study ($N = 20$), intended to provide preliminary data for future grant applications.

Data Analyses and Interpretation

Scores on the depression and trauma history questionnaires will be used as linear regressors to predict ratings of gentle brushing pleasantness.

Cold- and Affective-CPM: We will average the pain ratings from each stimulus period and compare the percent change of baseline to post-test ratings as our primary outcome measure. We will use ANOVA to compare differences between baseline and post-test between touch types, within or between dermatomes/segments, and between patients and healthy volunteers. A linear regression will be used to determine whether baseline touch pleasantness ratings significantly predict the CPM effect for each type of touch.

ASL/fMRI: Periods of baseline pain will be contrasted with periods of touch concurrent to pain (test) and following pain (post-test) in brain areas involved in pain processing. Connectivity analyses will be performed to identify the source of significantly reduced pain response in any of these areas during affective touch.

Inclusion of Women and Minorities:

Participants will include all genders and races. Based on the latest San Diego-based demographic consensus, we plan to recruit 60% White, 16% Asian, 7% Black, .5% Native American, .5% Pacific Islander, 12% Other race, 5% two or more races. We expect that 29% of our participants will be Hispanic or Latino. If necessary to obtain minority representation, under-represented racial groups will be targeted specifically for recruitment.

Rates of FM are higher in females than in males (9:1 ratio) [28], so an approximately 9:1 ratio is expected in the current study. All races and ethnicities will be invited to enroll. Expected demographics are based on the latest San Diego-area demographic census. If needed, to increase minority representation, recruitment efforts will include targeted advertising (e.g., flyers, postings, community outreach presentations) in communities with high minority populations and through community-based talks given by the PI and staff.

